4.4 Location

The AO imagers are housed in the FDA/CDRH/OSEL laboratory space on the White Oak Campus, Building 62, Room G238. The Heidelberg Spectralis high resolution OCT system and biometry device are in the same building, Room G101.

4.5 Study Duration

The duration of the study, including enrollment, data collection, analysis, and dissemination, is expected to last ten years. Follow-up visits will be allowed depending on the quality of the data collected and the availability of the participant. Each AO imaging session will occur within six months of a visit to the NEI. No more than three NEI clinical visits and five FDA AO imaging sessions will be performed in a year.

5.0 Data Management Plan

5.1 Storage of Data and Samples

No blood, tissue or other samples will be collected or stored in this study. Participant records from the NIH eye exams will be kept at the NIH eye clinic as described in Section 5.3. NIH clinical retinal images and data will be transferred to the FDA investigators only with participant consent. In general, the only NIH clinical information and data necessary to transfer to the FDA investigators will be the age and sex of the participant (to balance study demographic characteristics), lens status, ocular disease state and status, ocular axial length, fundus images, OCT images, and visual field maps. Section 4.2 describes the reasons this data needs to be shared with the FDA investigators. To protect participant's personal identifiable information (PII) and protected health information (PHI) and prevent its release to non-investigators, NIH clinical data (especially images) transferred to the FDA will be de-identified by the NIH by removing all PII, including name, address, social security number, and date-of-birth age. All NIH clinical data will be transferred by the FDA PI or Co-PI and stored only on a password protected Ironkey external hard drive (i.e., not transferred to an FDA computer) and kept in a locked file cabinet in the FDA PI's office ([name]). The external hard drive uses Data Locker software (FIPS 140-2 compliant) which meets all FDA and NIH IT requirements.

The only site of AO data and image collection will be the high-resolution imaging laboratory of FDA/CDRH/OSEL/DBP on the White Oak Campus. The acquired data will be initially stored on the AO system computers, which are password protected accessible only by study investigators. Because of the potential size of volumetric image datasets, which can be tens of gigabytes for a single participant for a single imaging session or more, data will be transferred to a dedicated server, which is password protected and accessible only by study investigators. All data collected at the FDA will be coded and will not contain any PII. AO images and data will be shared with the NIH/NEI co-PI and AIs for analysis and publication preparation. In general, the only data necessary to transfer from FDA to NIH will be processed images. The FDA AO data will be transferred to the NIH investigators via a password-protected Ironkey external hard drive and will be stored and accessed on the NIH CC EMR system or the NIH investigator's password protected (2-step authentication via PIV card) local computers. Since the images are already free of identifiable markers, there will be no need for de-identification.

5.2 Privacy

All research activities will be conducted in a private setting, with only the participant and investigators in the imaging laboratory.

5.3 Confidentiality

All records will be kept confidential and will only be reviewed by Drs. [name], [name], [name], and the NIH and FDA AIs. Electronic copies of the signed ICFs will be stored on the NIH CC EMR system. The Certificate of Confidentiality issued by the FDA in accordance with new requirements under the 21st Century Cures Act is included in Appendix 7.

For the NIH eye exam, records will be kept at the NIH eye clinic in the same manner as records from participants in other NIH-sponsored clinical studies. Information will be stored in the NIH's EMR system, which is accessible only by trained staff on password protected computers. Some information is collected in encrypted electronic records, which are stored on password protected computers. Except coded clinical data and retinal images discussed above in Section 5.1, all participant information remains on-site at the NIH eye clinic and is accessible only by trained staff and maintained with confidentiality abiding NIH policies and all relevant regulations regarding medical records.

For the FDA imaging session, a participant's name, age, and sex will be available to the FDA investigators to ensure a diverse population is represented, when age-matched participants are required, and to compare retinal images across different age groups. A participant number will be assigned to each participant and all information collected during the imaging session (image videos and ocular aberration data) will be coded using their participant number. Unlike clinical retinal images, AO images are not considered PII because the retinal patch imaged is too small (≤ 2 deg.) to reconstruct a complete map of retinal vasculature for participant identification and no medical diagnosis will be made using the AO images. The only link between participant number and PII (name, age, and sex) will be a single cross-referenced list, which will be kept in a password-protected excel spreadsheet. Any data publicly disclosed cannot be linked back to the participant. Only Drs. [name], [name], and [name] and the NIH and FDA AIs will have access to this electronic document.

5.4 Analysis Plan

De-identified AO data, particularly OCT and SLO videos will be analysed with custom software written by the investigators in LabVIEW and Matlab or commonly available image processing (ImageJ, Photoshop) and statistical programs. Examples of image processing and analysis code for AO applications include image registration, montaging or mosaic generation, capillary tortuosity and flow, and photoreceptor, RPE, and ganglion cell identification and quantification (cone packing, tessellation, Voronoi analysis). We may also work with collaborators external to this study on new analysis methods where de-identified participant data is shared. Because only de-identified information will be processed, a direct breach of confidentiality is not possible.

5.5 Data Sharing

De-identified AO images and other data from the study will be shared with internal and external professional colleagues, students, and other trainees during scientific and educational interactions. De-identified data at the NIH/NEI site may also be shared with collaborating laboratories at NIH or outside of NIH and/or submitted to NIH-designated repositories and databases. Repositories receiving data and/or samples from this protocol may be open-access or restricted access. Required approvals from the collaborating institution will be obtained and materials will be shipped in accordance with NIH and federal regulations.

Any new knowledge gained on disease mechanism, progression, diagnostic methods, clinical endpoints, and new disease biomarkers will be shared with the public in the form of peer-reviewed journal articles and public presentations at scientific conferences. Data sharing and participant engagement will be accomplished on an individual basis upon request. Upon IRB approval, the investigation will be registered on 'Clinicaltrials.gov'. Because this is an exploratory study on multiple disease types, the outcome measures reported to clinicaltrials.gov are not specified at this point. In general, for any AO structural or functional measure tested, we will compare results from a disease group and an age-matched control group. We will use all available resources (registries, websites, etc.) to share the results of this study with the public and patient advocacy groups. Confidentiality will be maintained through-out the reporting and data sharing process.

5.6 Quality Assurance

The FDA PI and co-PI will oversee the integrity and security of clinical data and images acquired within the purview of this protocol that are stored on the FDA campus. The NIH co-PI will oversee the integrity and security of clinical data and informed consents stored on the NIH EMR system. Quality assurance monitoring will be performed by the FDA PI at least annually. Quality assurance monitoring will include: a. Assuring that the patient spreadsheet is up-to-date and accurate; b. Assuring that all stored clinical data is de-identified, removed from any temporary locations, including the system computers, and archived properly on the dedicated server; and c. Assuring that all AO imaging data (which already contains no identifiable information) is archived properly on the dedicated server. The PIs and AIs will be responsible for the collection, processing, storage, retrieval, quality control and annotation of images and data collected during this study. All monitoring of the informed consent documents and process will be performed as specified in Section 3.9.

5.7 Study Conclusion

At the conclusion of the study, all FDA AO data will be removed from all computers and Ironkey external hard drives and archived on the dedicated server. Only the study investigators will have access to the dedicated server, which is housed in a locked FDA laboratory.

6.0 Patient Risks

6.1 Summary of Potential Risks

In general, there are three potential risks to the participants in this imaging study:

1. The participant has an allergic reaction or other complication to the mydriatic agent (increase in intraocular pressure),
2. The participant is exposed to a laser light level that exceeds the maximum permissible exposure (MPE) limit that damages the retina, or
3. The participant becomes injured during imaging from their presence in a research laboratory setting near scientific instrumentation.

Mydriatic drugs work by inhibition of the parasympathetic (i.e., contractive) response of the eye by blockage of muscarinic acetylcholine receptors or by stimulus of the sympathetic response of the eye by blockage of the re-uptake of noradrenaline. Side effects and complications associated with mydriatic drugs include photophobia, and in extremely rare cases, an increase in intraocular pressure leading to acute glaucoma. Mydriatic drugs are necessary for this investigation because the benefit from adaptive optics is optimal for dilated pupils larger than six (6) mm. Only those participants known (from clinical administration conducted by [name]) not to have severe adverse reactions to mydriatic agents will be enrolled in the study. All participants will experience some level of photophobia similar to that associated with a routine visit to their ophthalmologist. The effect of the drugs usually lasts four to six hours.

The second risk, light exposure to focused (ANSI) Class II or higher laser power levels, has to do with the interaction between imaging beams that are directed to the participant's eyes and their retina (the only reason the devices are minimally invasive rather than non-invasive). The laser safety analyses in Appendix 2a and 2b describe the technical details of the risk. Given the mitigation strategy, this risk has a very low likelihood of occurring but moderate severity if it does occur.

The third risk involves injuries that can occur when a participant unfamiliar with research enters a laboratory. The optics laboratory is not a wet lab, and so does not have harmful chemicals. The participant has one ingress/egress path to the AO imaging systems. Therefore, this risk has a very low likelihood of occurring and low severity if it does occur. This protocol and the imaging procedures described, as well as the eye exam, have been examined by the CDRH safety officer and found to be acceptable (Appendix 5).

6.2 Risk Mitigation Strategy

We will recommend that each participant avoids sunlight and wears sunglasses outside to mitigate photophobia. More severe complications (allergic reaction to mydriatic drugs) will be monitored by [name]

or the NIH/NEI AIs for 30 minutes after administration during the initial NIH eye exam and by the PI and co-PI during the FDA imaging sessions. The eye exam is designed to provide significant reduction in risk of reaction by screening participants with a predisposition or history of AACG.

The primary mitigation for the second risk is to maintain power levels that are below ANSI MPE limits. The power at the cornea will be measured each day an imaging session takes place and recorded in a logbook. The SLO and OCT illumination sources are superluminescent diodes (SLD), the output power of which are controlled from the computer. The SLD electronic drive boards have current limits that prevent excessive output power being delivered to the participant's eye. When SLDs fail, their power output will drop significantly or altogether (i.e., the power never increases for device failure). Scanner failure will direct a focused beam to the retina but also stop imaging, which will be nearly immediately noticed by the operator (within seconds), who can tell the participant to sit back from the instrument. The visible light stimulus source delivery is controlled with a shutter that precisely sets the illumination timing (pulse duration, etc.).

The third risk is mitigated by common laboratory safety practices that are in place at DBP and described in our BSC safety manual, which contains the emergency response plan as well as a description of procedures for dealing with chemical safety, biosafety, laser safety, and issues related to hazardous waste. OSEL complies with all Occupational Safety and Health Administration (OSHA) regulations and conducts routine safety training for its staff.

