4.1 Adaptive Optics Imagers

The AO imagers used in the study are investigational multimodal systems that includes OCT and SLO channels [13,14]. Two similar instruments will be used in the study. The first instrument, called the FDA mAO imager, scans two near-infrared wavelength beams, one centered at ~760 nm for SLO and one centered at ~830 nm for OCT, across the retina to produce images. The total power delivered to the retina for the mAO imager is below ANSI maximum permissible exposure limits, as described in Appendix 2a. The OCT channel in the second instrument uses a Fourier domain mode-locked laser (FDML). Therefore, the second is called the FDA AO-FDML imager, and uses three infrared beams at ~785 nm (SLO), ~850 nm (AO beacon), and ~1060 nm (OCT). The AO-FDML imager also includes a visible light stimulus channel for functional imaging experiments. The total power delivered to the retina for the AO-FDML imager is below ANSI maximum permissible exposure limits, as described Appendix 2b. The primary upgrade in the second instrument is the OCT imaging speed and pixel density, which has increased from 2.3 volumes (300×300 pixels) per second to 13.4 volumes (500×500 pixels) per second. In both instruments, ocular aberration sensing and correction is achieved with a Hartmann-Shack wavefront sensor (WS) and deformable mirror (ALPAO, DM97-08, France), respectively. Both instruments use a pupil camera and a fixation target to position the participant's head and eye for scanning a particular retinal region within 15 degrees from the fovea. Data collected generally include OCT and/or SLO videos; and less frequently WS videos (temporal sequences) and data on ocular aberrations. All patient procedures (alignment, fixation, imaging scans) and data formats used for the two FDA AO imagers are identical.

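### Section 6.2 answers a scanner failure only by having the operator notice it and ask the participant to sit back; cutting the imaging sources should be part of the stated response, per imager and per source.

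*Protocol*

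**What the plan says.** Section 6.1 lists laser exposure above the permissible limit as the second of three participant risks. It rates this risk as very unlikely, given the mitigation strategy, and moderate in severity. Section 6.2 then describes that strategy:

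- Main defence: "The primary mitigation for the second risk is to maintain power levels that are below ANSI MPE limits". Power at the cornea is measured and logged on every imaging day.
- Sources: "The SLO and OCT illumination sources are superluminescent diodes (SLD), the output power of which are controlled from the computer".
- Hardware cap: "The SLD electronic drive boards have current limits that prevent excessive output power being delivered to the participant's eye". The section adds that a failing SLD loses power and does not gain it.
- Scanner failure: "Scanner failure will direct a focused beam to the retina but also stop imaging, which will be nearly immediately noticed by the operator", followed by the parenthesis and response "within seconds), who can tell the participant to sit back from the instrument".
- Shutter: one is described, for the visible stimulus.

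Section 4.1 states for the first instrument: "The total power delivered to the retina for the mAO imager is below ANSI maximum permissible exposure limits". It says the same for the second instrument with reference to Appendix 2b. It also describes that second instrument's source: "The OCT channel in the second instrument uses a Fourier domain mode-locked laser (FDML").

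Section 4.3 says that the exposure time limits in Appendices 2a and 2b will be followed. Those appendices are listed in Section 10.0 but are not part of the text at hand.

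**The concern.** The response to scanner failure is a chain of human steps: the operator notices, the operator speaks, the participant moves. The verb is permissive (the operator can do this), and the only time given is an unnumbered count of seconds. Nothing in the chain acts on the light itself, although the paragraph has just said that SLD power is set from the computer.

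The other safeguards in the paragraph address different failures. The current limits cap power, and the argument that power falls concerns a failing diode. Neither responds to a scanner that has stopped while the source runs normally.

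The response matters because the low likelihood in Section 6.1 is stated to depend on the mitigation in Section 6.2. Participants are also chosen for good fixation and little head movement (Section 3.5) and are told to look at a target (Section 4.3). A stopped beam would therefore tend to stay on much the same retinal area until someone acts. The study is classified as greater than minimal risk (Section 6.3), and Cohort 2 already has outer retinal disease.

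**Working it through.** The protocol gives no figure to reproduce on this point, and no exposure calculation is possible. The body text contains no beam power, spot size, permissible-exposure value or stopped-beam time limit, and no response time beyond seconds. The check is a reading of Sections 4.1, 4.3, 6.1 and 6.2 together.

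**Step 1. Which stated safeguard acts when the scanner stops?**

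| Safeguard in Section 6.2 | Acts on a stopped scanner? |
|---|---|
| Power kept below ANSI limits, measured each imaging day | Yes, if the limit was set for a stopped beam; the body text does not say |
| SLD drive-board current limit | Caps power; does not end the exposure |
| Power falls when an SLD fails | A different failure |
| Computer control of SLD power | Could act, but is not tied to this failure |
| Shutter | Described for the visible stimulus only |
| Operator notices and asks participant to sit back | Yes; the only response stated |

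**Step 2. Does adding a source cut-off help, whatever the appendices say?** Let D be the time to notice, S the time to speak, M the time for the participant to move, and C the time to cut or block the source.

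- As stated, the exposure lasts D + S + M.
- With both actions started together, it lasts D + min(C, S + M).

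The second is never longer than the first, whatever the values, provided that operating the cut-off does not delay the spoken request. It is shorter whenever C is less than S + M. If software detects the loss of imaging, D may fall as well. The protocol gives no number for S, M or C and only an unnumbered count of seconds for D, so the direction is established and the size is not.

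**Step 3. Which beams does the computer-control statement cover?** Section 4.1 lists two imaging beams for the first instrument and three infrared beams for the second.

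| Imager | Beam (Section 4.1) | SLD statements in Section 6.2 |
|---|---|---|
| mAO | SLO, about 760 nm | Apply as written |
| mAO | OCT, about 830 nm | Apply as written |
| AO-FDML | SLO, about 785 nm | Apply as written |
| AO-FDML | AO beacon, about 850 nm | Not named in Section 6.2 |
| AO-FDML | OCT, about 1060 nm | Do not fit: the source is an FDML laser |

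Section 6.2 calls the OCT sources SLDs without distinguishing the instruments, which does not agree with Section 4.1. For the second imager's OCT beam, the body text therefore supports neither computer control of power, nor the current limit, nor the argument that power falls on failure.

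**Step 4. What depends on the missing appendices?** If Appendices 2a and 2b set their limits for a stopped beam over several seconds, asking the participant to sit back is a backup to a power level already within the limit. If they assume a moving beam, the response time carries the protection. The body text does not settle which applies.

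**The case against.** The strongest reply is that the hazard analysis lies in material not at hand. Sections 4.3 and 6.1 send the reader to Appendices 2a and 2b for exposure limits and technical detail, and Section 10.0 lists laser safety officer reviews of both analyses. If these already treat a stopped beam, the primary mitigation is sufficient and the sit-back request is only an extra. This stands: it rules out any claim that a limit is exceeded.

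Three further objections also stand:

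- Being controlled from the computer does not mean that the operator can end the exposure at once. Fast cut-off is an inference, and even the control statement is limited to SLDs.
- Section 6.2 does not present sitting back as the only permitted action. Nothing in it forbids cutting the source as well.
- Asking Section 6.2 to repeat an appendix figure would be a drafting preference, because the protocol already refers to the appendices.

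A reader might infer that participants would be overexposed, or that the stated response prolongs their exposure. The documents support neither. The first needs beam power and a stopped-beam limit, and the second needs a cut-off time to compare with; none of these is given. A concentration factor based on an assumed spot size would not help, since retinal hazard need not rise in proportion and no limit is available for comparison.

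The objections do not remove the comparison in step 2. Section 6.2 itself treats the stopped beam as something that needs a response, and a simultaneous cut-off can only shorten that exposure.

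**Conclusion.** The point holds as a low-cost improvement to a safety description, together with a request for confirmation. It is not a demonstrated error. Section 6.2 names a failure that leaves a focused beam on the retina, states a response that depends on the participant moving, and makes no use of the source control mentioned in the same paragraph.

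The benefit cannot be quantified from the protocol. It rests on two assumptions: that the sources can be switched off or blocked without delaying the spoken request, and that this can be done faster than a participant can be told and move. The first is plausible for the SLDs but not stated; for the FDML source the body text says nothing. Whether the present arrangement already suffices depends on Appendices 2a and 2b.

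**What to change.** Three changes:

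1. Amend Section 6.2 so that, on loss of imaging, the operator (or the acquisition software, if it is able to) switches off or blocks the imaging sources and at the same time asks the participant to sit back.
2. State this for each imager and each source. Reconcile the SLD description in Section 6.2 with the FDML source in Section 4.1, and have the sponsor confirm how that source is cut off. The AO beacon of the second imager, which Section 6.2 does not name, should be included in the list.
3. Have the sponsor confirm that the limits in Appendices 2a and 2b hold for a stopped beam over the seconds that Section 6.2 allows.

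The cost is one operating instruction and a few sentences of text. A software trigger would be additional work that cannot be priced from the protocol, and it is optional. The downside is an occasional false stop during a session.
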